The primary outcomes of this trial were to ascertain 1. The safety and AZM pharmacokinetic and 2. If treatment with AZM resulted in decreased nasal MMP-9 levels. Notably, when the study protocol was expanded to include non-ventilated patients, the primary outcome also changed from endotracheal MMP-9 to nasal MMP-9 levels. The secondary outcomes were to determine the *in vivo* efficacy of AZM administration on improving clinical outcome measures, specifically duration of ventilatory support and oxygenation, as well as PICU and hospital length of stay. The CONSORT guideline was used for the reporting of this trial.

Visit Schedule and Study Procedures

Overview:

If subjects met the inclusion criteria and have no contraindication to study participation, they were be enrolled into the study within 48 hours of positive pressure ventilation. Subjects were randomized via a permuted block design to receive either placebo (normal saline), 10mg/kg of IV azithromycin or 20 mg/kg of IV azithromycin, daily for 3 days. Prior to drug administration, assessment was performed to ensure that subjects do not have contraindications of AZM administration or development of any adverse events. Nasal and endotracheal aspirate (if

intubated) were obtained daily for the first 3 days (first sample obtained before drug administration).

Prior to drug administration, baseline labs (CBC with differential, liver and renal function, electrolytes) was reviewed. If the patient had evidence of hypokalemia, hypocalcemia or hypomagnesemia, the electrolyte abnormalities were corrected prior to drug administration. EKG was also reviewed, and if there was evidence of prolonged QT, the subject was excluded from the study. Vital signs (heart rate, blood pressure, temperature, saturations), ventilator or BiPAP or HFNC settings, presence of multi-organ failure were recorded. All these parameters were assessed prior to drug administration. Vital signs (heart rate, blood pressure, temperature, saturations) were also assessed immediately before the drug infusion, during, and 2 and 4 hours post completion of infusion.

During the hospitalization, all patients were treated according to the American Academy of Pediatrics guidelines for the management of bronchiolitis, namely supportive care. All decisions regarding medical treatment during hospitalization were made by the patient's primary care team.

Data Collection:

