Nasal, endotracheal aspirates (if intubated) and serum samples were obtained once daily for the first 3 days. The collection window had at least 24 hours between each sample collection. If patients were extubated within the first 3 days of study window, only nasal samples will be collected. Clinical data was collected each day until the subject was discharged from the ICU.

An overview of clinical and biologic data is outlined in this table.

	Day 1	Day 2	Day 3	Day of PICU discharge	Day of hospital discharge
AZM level (serum, nasal, lung)	X	X	X		
RSV titer (nasal and lung)	X	X	X		
Active MMP-9, Total MMP-9, TIMP (nasal and lung)	X	X	X		
Other RSV cytokine activity (nasal and lung)	X	X	X		
Continous vital signs monitoring ¹	X	X	X		
Baseline and continous lab review ²	X	X	X		
Electrocardiogram	X	X	X		
Study drug administration ³	X	X	X		
Duration of positive pressure ventilation (MV, BiPAP, HFNC)	X	X	X	X	X
Duration of oxygenation	X	X	X	X	X
Duration of PICU stay				X	
Duration of hospital stay					X

¹All assessments were done prior to dosing, during dosing until completion of infusion, immediately at the end of infusion, 2 and 4 hours post completion of infusion.

²Laboratories that were collected: CBC with differential, electrolytes, liver and renal function; record if done for clinical care.

³Study drug administration took place on 3 consecutive days (1 dose per day) after consenting. Study drug at 2 mg/ml was administered over 60 minutes.

Withdrawal of Participant Consent and Discontinuation of Study Drug:

Study participation may be discontinued for any of the following reasons:

- a. Subject decision to withdraw consent for study
- b. Evidence of allergy to administered products
- c. Intolerable adverse event as judged by study investigator

Safety Data

Adverse Events:

- a. Adverse event: Any untoward medical occurrence in a patient or clinical investigation in which a subject is given a pharmaceutical product; does not necessarily have a causal relationship with such treatment, or
- b. Any unfavorable and unintended sign (including abnormal laboratory findings), symptom, or disease temporally associated with the use of a medicinal (investigational) product; not necessarily related to the product.
- c. Change-from-baseline

AEs can take 2 forms:

- i. Appearance of a new symptom or sign, or
- ii. Increased severity or frequency of an existing symptom or sign

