This study was designed to have a total sample size of 48 participants divided into three groups, with 16 per group to detect a 25% and 37.5% decrease in lung MMP-9 activity in the treated groups (10mg/kg and 20mg/kg, respectively) relative to placebo with 80% power using analysis of variance. The assumptions were based on MMP-9 levels found in endotracheal aspirate of children with RSV-induced respiratory failure (Kong et al, *ERJ* 2014).

Means, standard deviations, medians, quartiles and range (minimum, maximum) described continuous variables and counts and percentages for categorical variables. To compare baseline characteristics among the treatment groups, we used Kruskal-Wallis test for age, height and weight due to evidence of non-normality of the distribution of the values. We used either Chi-Square or Fisher's exact test for categorical variables depending on expected cell counts.

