We analyzed inflammatory markers by first performing \log_{10} transformation to address the skewness of the distribution and extreme outliers. We then calculated the difference at each time point relative to baseline to obtain the change (i.e. pre and post treatment) outcome and fitted a generalized linear mixed model (GLMM) with random intercepts and assumed unequal variances across treatment groups with change from baseline as the outcome. The model included treatment, day and treatment by day interaction. Point and confidence interval estimates of the mean change outcome at each time point and treatment group combination were obtained. If a confidence interval for the mean change does not include 0, this is evidence of an effect associated with that particular treatment as it is either a significant increase (or decrease) in the inflammatory marker relative to baseline. The Bonferroni approach was used to adjust for multiple testing and simultaneous confidence intervals. Thus, significance was determined using a cut-off of 0.002 and a 99.8% level was used to construct confidence intervals for each for each treatment at each time point. Note that the sample size justification was based on the assumption that the MMP-9 levels are normally distributed with common standard deviation. However, in the data for this trial, we observed evidence of non-normality and non-constant variance across the treatment groups. Thus, GLMM was deemed more appropriate than ANOVA. Furthermore, fitting GLMM allows us to combine unbalanced data from different time points to help gain more power in evaluating treatment effect.

We used a generalized linear model assuming a negative binomial distribution for clinical outcomes (measured in number of days), using log link to address possible overdispersion due to some extreme observations. Furthermore, we fitted a model that allowed the variance to differ by treatment group. Spearman Correlation was used to examine associations. For this set of

analyses, the standard 5% level of significance and 95% confidence interval was used as these are all exploratory outcomes. All analyses were done using SAS version 9.4.

IRB and IND

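### The marker model uses the pre-dose value only by subtraction and writes out no contrast with placebo, so the comparison for which the trial was sized may be less precise than it could be

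*Combined protocol and SAP*

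**What the plan says.** All of the marker analysis is in the section Sample Size Determination and Statistical Analysis. Markers are log10 transformed, the pre-dose value is subtracted, and a mixed model with random intercepts and arm-specific variances is fitted "with change from baseline as the outcome". On the fixed effects it says: "The model included treatment, day and treatment by day interaction". No baseline term is listed there or in any other section.

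The decision rule is within arm: "If a confidence interval for the mean change does not include 0, this is evidence of an effect associated with that particular treatment". The cut-off is 0.002, with 99.8% intervals. No contrast between an active arm and placebo is written out.

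The sizing, in contrast, is comparative. The same section sizes 16 per group for decreases "relative to placebo with 80% power using analysis of variance", and the Data Analysis section also states its target relative to placebo. The mixed model is preferred to ANOVA because "we observed evidence of non-normality and non-constant variance across the treatment groups", and because it can "combine unbalanced data from different time points to help gain more power in evaluating treatment effect".

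A pre-dose value exists. Visit Schedule and Study Procedures describes daily sampling with the "first sample obtained before drug administration". Data Collection puts marker samples on days 1, 2 and 3, which leaves two follow-up days. Primary and Secondary Outcomes makes nasal MMP-9 the primary marker.

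**The concern.** Subtracting baseline fixes its coefficient at 1. When baseline and follow-up variances are equal, the coefficient that minimises the variance of a contrast is rho, so subtraction over-corrects whenever rho is below 1. With 16 children per arm, the pre-dose sample is an inexpensive further source of precision for a comparison that the plan itself says it wants to strengthen.

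The gain applies to contrasts with placebo, and the plan writes out none. Its rule asks whether an arm moved from its own starting point, which is not the question used for sizing. The two matters go together: the contrasts have to be specified before adjustment can help them.

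**Working it through.** **The plan's own figure.** The 16 per group cannot be reproduced, because no SD or significance level is given for the sizing. With an assumed alpha of 0.05, one-way ANOVA on means of 100, 75 and 62.5 (decreases of 25% and 37.5%) has 80% power at 16 per group if the SD is about 34% of the placebo mean. Nothing below depends on this.

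**Inputs.** From the documents: three arms of 16, a pre-dose value, follow-up on days 2 and 3, and variances allowed to differ by arm. Assumed: rho of 0.3, 0.5, 0.7 or 0.9, baseline SD of 1 in every arm, complete pairs, and one baseline slope per day.

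**Equal variances.** Per child, the variance factor is 2(1 − rho) for a change score and 1 − rho² with baseline as a covariate. The ratio is (1 + rho)/2. Estimating a common slope multiplies it by 1 + 1/(48 − 3 − 2) = 1 + 1/43.

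| rho | 0.3 | 0.5 | 0.7 | 0.9 |
|---|---|---|---|---|
| Contrast variance ratio, 16 pairs per arm | 0.665 | 0.767 | 0.870 | 0.972 |
| Square root (interval width) | 0.816 | 0.876 | 0.933 | 0.986 |
| Per-arm n for the change score to match, 16/ratio | 24.1 | 20.9 | 18.4 | 16.5 |
| Contrast variance ratio, 12 pairs per arm (1 + 1/31) | 0.671 | 0.774 | 0.877 | 0.981 |
| Within-arm mean change, 16 pairs | 0.777 | 0.845 | 0.913 | 0.981 |

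The last row is the quantity in the plan's written rule, taken at the pooled baseline mean: (1 + rho)/2 × (1 + (2/3)/43) + (1 − rho)/6.

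**Unequal variances.** Simulation used 100,000 trials per setting, 16 pairs per arm and a placebo follow-up SD of 1. The common slope was weighted by the estimated residual variance of each arm. Entries are variance ratios for a contrast with placebo.

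| Follow-up SD in the active arms | 0.3 | 0.5 | 0.7 | 0.9 |
|---|---|---|---|---|
| Both 0.67, common slope | 0.55 | 0.63 | 0.71 | 0.78 |
| Both 1.5, common slope | 0.81 | 0.92 | 1.01 | 1.00 |
| 0.67 and 1.5, narrower arm, common slope | 0.56 | 0.64 | 0.72 | 0.77 |
| 0.67 and 1.5, wider arm, common slope | 0.81 | 0.94 | 1.08 | 1.31 |
| 0.67 and 1.5, wider arm, arm-specific slopes | 0.83 | 0.94 | 1.02 | 0.96 |
| Both 1 (equal variances), arm-specific slopes | 0.69 | 0.79 | 0.89 | 1.00 |

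Six patterns were examined for the two active arms: (1, 1), (0.67, 0.67), (1.5, 1.5), (1, 1.5), (1, 0.67) and (0.67, 1.5). Over all six, arm-specific slopes gave contrast ratios from 0.566 to 1.021 and a within-arm ratio of at most 1.05. With a common slope, a single arm's within-arm ratio reached 1.27. These ranges describe the patterns tried and are not bounds.

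**Few pairs.** Endotracheal samples exist only while a child is intubated, and the number of such pairs is not given. At an assumed 6 pairs per arm with equal variances, the common-slope ratios are about 0.72, 0.84, 0.94 and 1.05, and the arm-specific ratios about 0.79, 0.92, 1.05 and 1.15. At 5 pairs, arm-specific slopes give about 0.88, 1.00, 1.11 and 1.27. At 5 to 6 pairs and rho 0.9, the common slope loses about 5% to 10%.

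**The case against.** The strongest reply is that nothing here is an error. Log10 change with arm-specific variances is a valid analysis. Rho is unknown. The plan reports unequal variances, so the equal-variance figures describe the case that it says did not hold. A common slope can then lose precision. The trial is also complete, so choosing a covariate now is post hoc, and fitting several versions adds analytic flexibility.

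Much of this stands. It limits the claim to efficiency, makes the size conditional, and requires a post hoc label and a stated error level. It does not remove the point. Rho can be estimated from data already in hand, and with 16 pairs arm-specific slopes added at most about 2% to any contrast variance in the patterns examined. The placebo contrasts are needed in any case to answer the question used for sizing.

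A second reply is that endotracheal markers may have too few pairs. That is right, and the fix is narrowed accordingly.

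A reader might also infer that a chance baseline gap biases the change-score contrast. It does not. Conditionally, the contrast carries a share (1 − rho) of such a gap (equal variances), but over randomisations this is the same extra variance already counted, not a second defect.

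**Conclusion.** The point holds as a possible and avoidable loss of precision, at the level of something the analysis should do rather than must do. With 12 to 16 complete pairs per arm and equal variances, adjustment removes about a third of the contrast variance at rho 0.3, just under a quarter at 0.5, about an eighth at 0.7 and almost nothing at 0.9. With 16 pairs, intervals are about 18%, 12%, 7% and 1% narrower.

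Two stronger readings are not supported. One is that adjustment always helps: with unequal variances a common slope ran from about 0.55 to 1.3, the losses coming at high rho. The other is that the planned analysis is invalid or the trial demonstrably underpowered because of this. The documents give no rho, SD or sizing alpha from which that could be shown. Confidence is medium, because the size rests on an assumed rho and assumed variance patterns.

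**What to change.** For the nasal markers, including the primary nasal MMP-9:

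- Write out each active arm versus placebo on each follow-up day (2 arms × 2 days = 4 contrasts per marker).
- Add the log10 baseline of the same marker and baseline-by-day to the mixed model, keeping variances unequal by arm.
- As a check on the common slope, also fit baseline slopes that differ by arm, with baseline centred at the pooled mean.
- Report these contrasts beside the unadjusted result, labelled post hoc. Either give 95% intervals stated to be exploratory, or state the multiplicity level used and how it relates to the existing 0.002 cut-off.

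For endotracheal markers, do not use arm-specific slopes. Add a common baseline slope only if there are enough complete pairs, and report how many there are.

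The cost is one rerun on samples already collected. A common slope on each of two days takes about two degrees of freedom, and arm-specific slopes take six. Arm-specific slopes give up about 2 percentage points of the gain when variances are equal. The main risk is that a common slope loses precision on one contrast when the active arms' variances differ from placebo in opposite directions and rho is high, by up to 31% in the patterns examined. The arm-specific fit is there to reveal this.

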Prospective Pilot Clinical Trial of
Azithromycin Treatment in RSV Induced
Respiratory Failure in Children

Study Protocol & Statistical
Analysis Plan

NCT02707523

October 10, 2019

[name]., Principal Investigator
University of Alabama at Birmingham
Birmingham, AL 35294

Study Protocol:

Design

The study was a double-masked, placebo-controlled phase 2 trial with 3 treatment groups (ClinicalTrials.gov NCT02707523). All subjects, their families, medical providers, and study staff were blinded to study medication allocation, with the exception of the biostatistician and the pharmacist.

Recruitment and Enrollment

Subject Recruitment:

16 patients per group [placebo (saline), 10mg/kg azithromycin and 20mg/kg azithromycin group; total=48] were recruited from the Pediatric Intensive Care Unit (PICU) at Children's of Alabama. All children with RSV infection and required positive pressure ventilation (invasive and non-invasive) were screened for eligibility.

Patient Compensation:

None

Race and ethnicity:

The race and ethnicity were classified based on either patient self-identification or by hospital staff during admission. Race and ethnicity were assessed in the study to provide a baseline characterization of patients cared for in this region.

Eligibility/Inclusion Criteria:

Inclusion Criteria:

1. Admission to the PICU at Children's of Alabama with a diagnosis of RSV infection and requiring positive pressure ventilation (invasive and non-invasive). Non-invasive positive pressure ventilation is defined as need for BiPAP (bilevel positive airway pressure) or high flow oxygen (namely, >1 L/kg/min of flow, with a minimum of 5 L/min flow for children <5 kg).
2. Enrollment into the study within 48 hours of ICU admission and placement on positive pressure ventilation
3. Age 0-16 years

Exclusion Criteria:

1. AZM use within 7 days of PICU admission
2. Contraindication to AZM use
 - Patients with electrocardiogram QT interval corrected for heart rate (Qtc) ≥ 450 ms
 - Patients with significant hepatic impairment (direct bilirubin >1.5 mg/dL)
 - Known hypersensitivity to azithromycin, erythromycin, any macrolide, or ketolide drug
 - Cardiac arrhythmia
3. History of pyloric stenosis
4. Patients requiring chemotherapy or on chronic steroids for malignancy or post bone marrow transplantation
5. Positive pressure ventilation greater than 48 hours prior to PICU admission

Informed Consent:

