Consent was obtained in a quiet setting prior to the initiation of the study. The legal guardian was given opportunity to delay consent until he/she has taken adequate time to read and understand the written consent and discuss the study with others. Subjects were not consented in writing

until they were able to demonstrate adequate understanding of all aspects of the study and consent process. A copy of the consent form was given to the patient/legal guardian. The signed consent form remained in the patient's study files at the clinical center.

Randomization:

All enrolled subjects were randomized according to a permuted-block design to receive either placebo (saline) or AZM (Fresenius Kabi, USA) at 10mg/kg/day (referred to as "standard dose") or 20mg/kg/day (referred to as 'high dose') intravenously (IV) every 24 hours for 3 days. The randomization schedule was created by the study biostatistician and provided to the study pharmacist for implementation. The FDA required the study enrollment to be done in two stages, Stage 1: First 9 subjects (older than 6 months), and Stage 2: Remaining 39 subjects (of all ages) if no safety issues were found. The first stage enrolled 9 subjects equally to the 3 treatment groups. For this, the random assignment of treatment was determined by random permutation. For the second stage, we randomly assigned the 3 treatments equally to the 39 subjects using block randomization of size 3 or 6. In addition, to maintain blinding to the treatment assignment, placebo was randomly assigned to either 10 mg/kg or 20 mg/kg dose. [name] generated the randomization schedule as described above. [name] provided the randomization schedule (with randomization IDs) in an excel file to the study pharmacist in charge of dispensing the appropriate treatment.

Duration of Study:

The trial began in February of 2016, and due to the age restriction placed by the FDA, the first 9 subjects enrolled were older than 6 months of age. Once this number was attained, and no safety

concerns were evident as determined by the DSMB, infants younger than 6 months of age were eligible for enrollment in the study. The study spanned three and a half RSV seasons, with the last patient enrolled in February of 2019. The trial ended once 48 subjects were enrolled into the study. All subjects completed the study. No long term follow up was provided.

Primary and Secondary Outcomes

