All participant data were obtained and recorded in individual files that was stored in a secured file cabinet within a locked office. Upon study entry, all participants were given a unique identifier to be used through the entirety of the study and this too was maintained in a locked file cabinet in secured office. Following each study visit, the data obtained was entered into a database using the study participants' unique identifiers. All other personal data were omitted from electronic records. At the close of the study, any missing data was verified with chart review. Only authorized study personnel have access to patient data.

Data Analysis

The primary outcome measured was MMP-9 activity. Based on our preliminary data, we expect that n=16 per group would be sufficient to detect a 20% and 25% decrease in MMP-9 activity in the treated group (10mg/kg and 20mg/kg; respectively) relative to placebo with 80% power.

[name] (Professor, UAB School of Public Health) is the biostatistician for this clinical trial.

Nasal and Endotracheal Aspirate Collection and Processing

Nasal samples were collected using a nasal swab inserted through the nares parallel to the palate (not upwards) until resistance was encountered or the distance inserted was equivalent to that from the nostril to the ear of the patient indicating contact with the nasopharynx. After gentle rubbing and rolling of the swab, it was left in place for several seconds to absorb secretions prior to removal. The swab was then immediately placed into a sterile vial containing 3 ml of viral transport media (Quidel, San Diego, CA), and kept at 4°C for further analysis.

Endotracheal aspirates were collected via endotracheal tube suctioning using an 8 Fr suction cannula (CareFusion, San Diego, CA, USA) and centrifuged at 500xg for 10 min to separate supernatant from cells and mucus (pellet) . Separate aliquots of supernatant were subsequently saved at 4°C for further analysis.

Assay of AZM, Urea and Pharmacokinetic Analysis

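### Support mode at enrolment is neither balanced by the randomisation nor listed in any outcome model, so the day-count comparisons are exposed to chance imbalance and avoidable variance

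*Combined protocol and SAP*

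**What the plan says.** All places are in the combined protocol and SAP.

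- **Eligibility/Inclusion Criteria** takes children "requiring positive pressure ventilation (invasive and non-invasive"; BiPAP and high flow count as non-invasive. **Primary and Secondary Outcomes** refers to the time "when the study protocol was expanded to include non-ventilated patients". Since positive pressure support is still required, this presumably means children who were not intubated.
- **Randomization** describes two stages: 9 children older than 6 months assigned by random permutation, then 39 children of all ages in blocks of 3 or 6. Of Stage 1 it says "The first stage enrolled 9 subjects equally to the 3 treatment groups", and Stage 2 is also allocated equally. No stratification by support mode or age is described.
- **Visit Schedule and Study Procedures** has ventilator, BiPAP or high-flow settings recorded before the drug is given.
- **Sample Size Determination and Statistical Analysis** gives the marker model, with log10 change from baseline as outcome: "The model included treatment, day and treatment by day interaction". For durations: "We used a generalized linear model assuming a negative binomial distribution for clinical outcomes (measured in number of days". That model lets the variance differ by arm, but no baseline covariate is named. Age, height, weight and categorical characteristics are compared across arms, and none is said to enter an outcome model. The 5% level is used for the duration analyses because they are called exploratory.

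**The concern.** Days of mechanical ventilation, days of BiPAP or high flow, oxygen days, PICU stay and hospital stay all depend on how sick the child is at entry, and support mode is the most direct recorded marker of that. For days of mechanical ventilation the link is built in: an intubated child is already accruing days, while a child on BiPAP or high flow contributes days only if intubated later.

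Two things are at stake. First, in the single realised sample, an uneven split of intubated children between arms can imitate or mask a treatment effect on days, and comparing baseline characteristics does not correct for this. Second, even with an even split, the spread between modes stays in the residual variance and widens every between-arm interval. With arms this small, neither effect is negligible if support mode is strongly prognostic.

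**Working it through.** **Inputs from the documents.** Three equal arms: "total sample size of 48 participants divided into three groups, with 16 per group". Stage 1 has 9 children and Stage 2 has 39. The share intubated, the prognostic strength of support mode, mean days and dispersion are not given, so they are assumed below and varied where shown. The plan's power statement does not help: it concerns lung MMP-9, gives no standard deviation, and so cannot be reproduced or carried over to day counts.

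**1. Stage.** 9/3 = 3 and 39/3 = 13 per arm; 3 + 13 = 16, which reproduces the stated arm size. The between-arm difference in stage is exactly 0.

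**2. Chance imbalance in support mode.** Let X1 and X2 be independent Binomial(16, p) counts of intubated children in two given arms. Summing the joint probabilities over |X1 − X2| ≥ 4:

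- p = 0.3 or 0.7: 0.175
- p = 0.5: 0.215

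For at least one pair among the three arms, the probability is 0.36 at p = 0.3 and 0.43 at p = 0.5.

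**3. What a split of 6 versus 10 intubated does by itself.** With no treatment effect, and intubated children having r times the mean days, the ratio of arm means is (6r + 10)/(10r + 6):

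- r = 1.5: 19/21 = 0.90
- r = 2: 22/26 = 0.85
- r = 3: 28/36 = 0.78

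**4. Variance and power.** Simulation settings: negative binomial, 3 × 16 children, 50% intubated, mean 4 days if not intubated, dispersion k of 0.15 or 0.30, true ratio 0.65 in one arm, fitted with and without support mode. There were 1,500 trials per setting; the power figures at r = 1.5 come from a separate run of 1,000.

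A large-sample formula gives a hand check. Per arm, with μ averaged over the two modes, the variance of the log mean is proportional to

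- unadjusted: [mean(μ + kμ²) + var(μ)] / mean(μ)²
- adjusted: 1 / mean[μ/(1 + kμ)]

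For r = 2 and k = 0.15, the reference arm has μ = 4 and 8:

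- unadjusted: (6 + 0.15 × 40 + 4)/36 = 0.444
- adjusted: 1/[(4/1.6 + 8/2.2)/2] = 0.326

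The arm with ratio 0.65 has μ = 2.6 and 5.2:

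- unadjusted: 8.125/15.21 = 0.534
- adjusted: 1/[(2.6/1.39 + 5.2/1.78)/2] = 0.417

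The ratio is (0.444 + 0.534)/(0.326 + 0.417) = 1.32. The same steps with k = 0.30 give 1.25.

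| r | Variance inflation, simulated | Large-sample formula | Power, unadjusted to adjusted, k = 0.15 | Same, k = 0.30 |
|---|---|---|---|---|
| 1.5 | 2–10% | 8–10% | 46% to 50% | 36% to 38% |
| 2 | 26% | 25–32% | 46% to 54% | 37% to 42% |
| 3 | 62–82% | 60–80% | 39% to 58% | 31% to 44% |

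The formula ignores small-sample effects, so it should agree only approximately, and it does.

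**5. Weak prognosis.** On a linear scale with 50% intubated and a mode effect of d residual SDs, R² = 0.25d²/(1 + 0.25d²), and the adjusted standard error is √(1 − R²) times the unadjusted one: 0.970 at d = 0.5 and 0.894 at d = 1.

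**6. Omitting stage.** In a linear simulation (20,000 trials, no treatment effect, 1-SD stage effect), the unadjusted contrast has a true SD of 0.353. The mean estimated standard error is 0.379, and type I error is 3.5% against a nominal 5%.

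**The case against.** Randomisation already protects the comparison: averaged over allocations, unadjusted contrasts are unbiased. In a linear simulation with an omitted 1-SD mode effect and 40% intubated, bias was about 0 and type I error 4.9%. The durations are secondary and labelled exploratory, and every size given above rests on an assumed prognostic strength; at a ratio of 1.5 the gain is slight. All of this stands. It limits the point to efficiency and to imbalance in the one realised sample.

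Four stronger readings are tempting, and the documents do not support them.

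- *Ignoring stage lets the arms become unbalanced.* Equal allocation within each stage rules this out.
- *Age above or below 6 months stands in for stage.* Only Stage 1 had that age limit; Stage 2 took all ages, so children over 6 months can be in both stages.
- *The primary marker result is undermined.* The stated marker rule asks whether each arm's interval for change excludes 0, and no between-arm marker contrast is written out. Change from baseline also removes stable differences in level between support modes, so mode matters there only if it predicts the change.
- *The plan excludes covariates from the duration models.* The text names none, so their absence is inferred from silence.

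**Conclusion.** The point holds for the day-count outcomes. Support mode at enrolment is recorded and probably prognostic, yet the described randomisation does not balance it and no described model uses it. The chance that two given arms differ by 4 or more intubated children is about 18–22%, assuming 30–70% are intubated. The variance cost is about 2–10%, 26% or 62–82% for assumed ratios of 1.5, 2 or 3 in mean days. The omission is clear from the text. Its size is not, because the documents give neither the share intubated nor the prognostic strength.

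Stage belongs in the model because allocation was restricted by it, but leaving it out only overstates the standard error. For the markers the case is weaker. A reader should not infer that the unadjusted analyses are invalid; they are less precise than the recorded data allow, and harder to interpret if the realised split is uneven.

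**What to change.** - In each negative binomial model for a day-count outcome, add support mode at enrolment (invasive versus BiPAP or high flow) and randomisation stage as baseline terms. Age may be added as a separate optional covariate, not as a substitute for stage.
- Report the adjusted arm contrasts beside the unadjusted ones. The document is dated October 2019, after the last enrolment in February 2019, the biostatistician was not blinded, and the analysis section describes features of the trial data. If the terms are chosen after unblinded data were seen, label the adjusted contrasts post hoc.
- Tabulate support mode at enrolment by arm.
- In the marker mixed model, add the same two terms for any between-arm contrast that is reported, expecting a smaller gain.

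The cost is one or two degrees of freedom per model and no new data. If neither term is prognostic, the 95% interval from a linear model with both added is about 1.001 times as wide as without them.
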